5. STUDY DESIGN AND SCHEDULE

A. LOCATION

Visits will be done at the University of North Carolina-Chapel Hill Food Allergy Study Center (FASC), located in the CTRC building. The FASC is equipped as a clinic. In addition to MD and NP coverage, there are 24-hour adult and pediatric rapid response teams in case of emergencies. The study

site is adjacent to the UNC Hospitals Emergency Department where subjects can be transferred for continued monitoring and acute care as needed.

B. DURATION OF ENROLLMENT

The study enrollment duration is for 2 years or until a commercial peanut OIT products is available to participants whichever is sooner.

C. DURATION OF THE STUDY PER PARTICIPANT

Each participant will be in the study for a total of 12 months. There will be three phases in the study: escalation phase for 1 day, build up phase up to 16 weeks, and maintenance phase up to 3 months on peanut OIT followed by 6 months of food equivalent to tolerated peanut protein.

D. STUDY VISITS

Participants will have: an initial study visit (screening), followed by one visit for the escalation phase, followed by visits every 1-2 weeks for the up dosing phase, a visit at the end of peanut OIT treatment at 6 months, a phone interview at 9 months and a final visit at the end of the study at 12 months. The screening visit may be combined with the initial escalation visit.

1. SCREENING AND BASELINE VISIT

We will perform screening during the initial study visit. We will determine if the patient is still eligible for the study, discuss the study and consent with the patient, perform physical exam and spirometry (participants \geq 7 years old). A blood draw and skin prick test may also be performed.

2. ESCALATION PHASE

All subjects will undergo a one-day peanut desensitization protocol to enable them to tolerate a daily dose of peanut protein (3-6 mg) (Table I). If the participant has a reaction to one of the doses in the escalation, the next dose will be determined at the discretion of the investigator. The options open to the investigator are to administer the last previously tolerated dose, or wait an additional amount of time between doses. Once this determination of the dosage amount is made, the desensitization process resumes as outlined.

Upon completion of the modified escalation phase to peanut, the subject is observed for a minimum of 2 hours. If there is no evidence of an allergic reaction the subject is discharged home. If the subject requires treatment for symptoms during the initial escalation protocol with antihistamines on one occasion, then the rest of the protocol may be followed. If the subject requires more than one medication or multiple doses of antihistamines or requires other rescue medications, the initial desensitization phase should be stopped. If the subject has tolerated either the 3 mg or 6mg dose, the subject will be eligible to return on Day 2 to proceed with the build-up phase. Subjects must be able to tolerate the first two doses of escalation with mild or no symptoms to continue with build-up.

Table I

Dose #	Dose	Interval (minutes)	% Increase
1	1.5mg	30	100
2	1.5mg	30	0
3	3mg	30	100
4	6mg	30	100

3. BUILD UP PHASE

After the first day of desensitization, subjects will return to the research unit the following day to begin the build-up phase of the study. The subject will ingest 6 mg, or a lower amount based on the reaction during the escalation phase. After the subject is observed for a minimum of 30 minutes for symptoms to the study protein ingestion, he or she will be discharged from the research unit and will continue to consume the study protein at home daily fourteen days (-3/+7 days). The family receives the study protein doses as a powder that they give to the child each day by sprinkling it on a previously tolerated food (e.g., apple sauce). Subsequently, subjects will return to the clinical research unit every 2 weeks (-3/+7 days) to monitor their adherence to the dosage administration and increase the dose to the next escalation amount (Table II). Vital signs are performed prior to the dose administration, prior to the completion of the observation period before discharge, and anytime symptoms occur. If the study team feels that a longer observation time is warranted based on the prior dosing history of the subject or their current physical status, the subject will be observed for a longer period of time. If symptoms occur that do not require treatment, the subject will

be observed until they resolve. If symptoms occur that require diphenhydramine or albuterol, the subject will be observed a minimum of 2 hours or until symptoms resolve. If symptoms occur that require epinephrine, the subject will be observed at least 4 hours or until symptoms resolve. If symptoms do not fully resolve after 6 hours or if new symptoms occur, the subject will be transferred to UNC Children's Hospital to be observed overnight. Per individual stopping rules, participants experiencing severe symptoms during buildup will be terminated from the study.

Subjects who tolerate dose escalations will take that dose daily for a period 2 weeks (-3/+7 days) after which they will return to the clinical research unit to have the daily dose increased proportionately at each visit until the maximum daily dose of study protein (300 mg) is reached. Mechanistic studies may be done at the discretion of investigator to address any clinical symptoms for further studies.

Table II

Dose #	Dose	Interval(weeks)
5	6mg	Day 2
6	12mg	2
7	25mg	2
8	50mg	2
9	75mg	2
10	100mg	2
11	150mg	2
12	225mg	2
13	300mg	2

4. MAINTENANCE PHASE

After completing build up phase to 300 mg study protein, the subjects will continue to receive their maintenance dose of study protein daily for the proceeding 3 months of the study (maintenance phase). After 3 months of maintenance, the subject may have mechanistic studies done at end of study visit. Data from our previous studies indicate that home dosing is safe, with infrequent

reactions which are typically mild. These data have identified several risk factors for reactions, which include dosing on an empty stomach, fever/illness, and activity/exercise shortly before or after dosing. Families of subjects will be asked to administer the study protein with additional food such as at snack or meal times, and will be instructed to hold the dose during illness and contact study personnel for instruction. After 3 months of daily maintenance peanut protein OIT, subjects will have a follow up visit where they are assessed by study investigator and if qualified they will be switched to food equivalent of peanut protein for the following 6 months.

5. PEANUT FOOD EQUIVALENT PHASE

At the end of maintenance peanut OIT phase, subjects will be given instruction during their last study visit in maintenance phase to start a peanut food equivalent of 300 mg peanut protein: which include the following options: peanuts (not dry roasted), peanut butter, powdered peanut butter, mini snickers, mini Reese's cup, cheese peanut butter crackers, Reese's pieces, Reese's peanut butter chips or Goober. An instruction sheet will be provided on how much to take of one of these products on a daily basis. This phase will last for 6 months. During this phase, subjects will continue to fill compliance sheets and they will receive phone calls from study coordinators at 9 months. This will be no study visits until the end of this phase to hand daily compliance sheets and fill a survey. At the end of the study the subjects may have the option to enroll in our peanut OIT follow up study if study investigator deemed they meet inclusion criteria for the study.

E. HANDLING ADVERSE REACTIONS AND FOLLOW UP DURING HOME DOSING

Each subject is given multiple ways to contact study staff when they are enrolled in the study. This is reviewed at the end of each visit. The families are told to contact the study staff if they have any questions or concerns before the next visit or at any time during the study. Study contact information given to families include the research clinic phone number, email addresses and office numbers of the, study coordinators, and instructions for how to get in contact with the pediatric on-call allergist who can reach the lead coordinator if needed. Subjects who have any symptoms during observed dosing, or those who express any specific concerns are given a follow up phone call on the day after dose escalation. All subjects will be asked to carry an auto-injector epinephrine. If prescription is not provided by their physician, we will provide them with a prescription for an auto-injector epinephrine. We will ask subjects to fill their prescription and

bring their epinephrine auto-injector with them before starting treatment to verify they have filled their prescription.

F. MANAGING MISSED DOSES

Subjects who miss one to two days of the daily dose will continue at their current dose at home. The PI will determine where the next dose of study protein is given for those who miss three to four days of the daily dose based on the length of time on study, the daily dose amount, the subject's reaction history and the amount of time since the last reaction to a dose in order to assure safety with dosing. Those who miss more than four consecutive days will return to the clinical research unit for evaluation by the study team in order to determine the best course of action for the subject. Options open to the investigator include repeat desensitization, observed dosing at the current level, or observed dosing at a dosing level previously tolerated by the subject. All such management of missed doses will be carefully documented in the study database.

G. MONITORING OF SIDE-EFFECTS, ADVERSE EVENTS, AND CLINICAL CHANGES

- We will monitor accidental reactions to peanuts in each subject during each visit to the study center. We will note any reaction that occurs in a subject within two hours after the ingestion of peanuts, and record the type of symptoms (i.e., skin, respiratory, gastrointestinal, or cardiovascular). A copy of the CRF is in the appendix.
- To monitor subjects for adherence, any accidental ingestion, any symptoms related to daily dosing and any unintended side-effects of daily dosing, the families will be asked to keep a simple daily diary to record the requested information. A copy of the daily diary is included in the appendix of the protocol.
- We will check mechanistic changes in the immune system by checking lab tests, skin testing or spirometry during the study.

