6. The participant experiences severe symptoms during the build-up or maintenance phases as a result peanut OIT dosing

7. In the investigator's discretion, there is poor compliance or any other concern that would create an unacceptable risk to the subject.

8. The participant dies.

9. The study ends.

To the extent possible, participants who discontinue therapy will be followed to observe and record study outcomes.

D. STUDY TERMINATION CRITERIA

If any of the stopping rules listed below are met, study enrollment will be suspended, the initial dose escalation phase and build-up phase will be stopped, and all enrolled participants will remain on their current dose pending expedited review of all pertinent data by the Data Safety Monitoring Board:

1. Any death related to peanut OIT dosing.
2. More than one event comprising systemic allergic symptoms with significant hypotension at any stage of the protocol.
3. More than 3 participants require more than 2 injections of epinephrine during dosing of the peanut product.
4. More than 3 of the following events:
 - Severe adverse event, other than anaphylaxis, related to investigational product.
 - Eosinophilic esophagitis.

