Afterwards, if clinical indicated, spirometry will be administered per clinic asthma standard of care as an assessment of lung function in subjects 7 years of age or older during study visits. Procedures follow American Thoracic Society criteria. Bronchodilation is not conducted and beta-agonists do not need to be withheld prior to the test. The test is administered while the subject is in a standing position and using a nose clip. We will reference the Hankinson predictive values for lung function. Subjects between 7 and 11 years who are unable to perform spirometry will be offered an attempt to use a peak flow meter. Participants who are unable to maintain >80% PEFR of their predicted value will need to be evaluated by the NP or MD before proceeding.

E. SALIVA COLLECTION (OPTIONAL-SUBJECT TO THE INVESTIGATOR DISCRETION)

A 0.5 ml of saliva could be collected to run mechanistic assays as determined by the investigator. Examples include: checking mechanistic studies for subjects who develop specific gastrointestinal side effects (e.g. EoE), subjects who are unable to tolerate desensitization to 300 mg or subjects with severe adverse events.

Samples may be obtained by the subject spitting independently or the coordinator using a plastic syringe to gather saliva.

F. COMPLIANCE SHEETS

Subjects will be given sheets to record their compliance with the medication that needs to be changed on a weekly basis. The sheets will also include reactions the subjects have, the symptoms they experienced and how they were treated. Subjects will hand the sheets to their study coordinator at each visit and at the end of the study. The data from these sheets will be used to assess compliance and adverse events in addition to information gathered from subjects from their follow up surveys.

G. URINE PREGNANCY TEST

All participating females of child bearing age will have pregnancy urine test in screening then for the last follow up visit within 30 days of the last pregnancy test. Female subjects who become pregnant will be taken out of the study. Sexual abstinence will be accepted as an effective method of

contraception.

Sexually active female subjects are to use either:

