10. STATISTICAL CONSIDERATIONS AND ANALYSIS STRATEGY

A. INTERIM AND FINAL ANALYSES

An interim analysis will be performed when at least 50 patients have finished their peanut OIT treatment phase and at least 25 patients finished 6 months of food equivalent treatment phase.

The interim analysis and the final analyses will include all subjects in the study who provided complete follow up information regarding their

compliance and adverse events, and will also include those who dropped out or were withdrawn from the study before its completion.

The final analyses will be performed when all subjects have completed the study.

B. PLANS FOR EACH SPECIFIC AIM

Aim 1. Investigate the safety and compliance in the 2-stage protocol in subjects who either (a) have previously developed desensitization and then subsequently lost this protection due to a period of time off of therapy, or (b) have previously endured an extended time on placebo therapy.

We will rely on the following methods to accomplish Aim 1:

1. Our primary analysis will focus on estimates of incidence rates of adverse events and the proportion of days of treatment missed during the treatment protocol.
2. Our secondary analyses will include estimation of
 - the overall incidence rate of gastrointestinal AEs during the entire 2-stage treatment sequence.
 - the overall incidence rate of Epipen use
 - the overall incidence rate of drop-outs due to gastrointestinal AEs during the entire 2-stage treatment sequence.
3. Exploratory analyses will be used to investigate potential candidate risk factors for AEs (using logistic regression models) and causes of missed treatment days (using generalized log-linear models for counts of days).
4. Descriptive tabular and graphical methods will be used to visualize the data and examine the relationships among the measures of interest using graphical and descriptive methods.

All statistical estimates will be tabulated with the corresponding 95% confidence intervals (CI). Interpretation of these CIs will be an integral part of the analyses. For Aim 1 (and for all the aims) sensitivity analyses will be performed to evaluate the robustness of the main results to reasonable perturbations of the choices of statistical methods and statistical assumptions used. For example, the influence of any extreme or questionable data value will be explored. Results of the sensitivity analyses will only be used to guide our level of confidence in the main results.

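### Food-stage daily sheets have one scheduled hand-in, at month 12, and no step retrieves them from a participant who withdraws or is lost before then

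*Combined protocol and SAP*

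**What the plan says.** All references are to the combined protocol and SAP.

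- **Stage length (5.D.5).** "This phase will last for 6 months".
- **Collection in the food stage (5.D.5).** "This will be no study visits until the end of this phase to hand daily compliance sheets and fill a survey".
- **Contact in between.** 5.D.5 says "they will receive phone calls from study coordinators at 9 months". The visit list in 5.D gives "a phone interview at 9 months and a final visit at the end of the study at 12 months". Neither says what is recorded at the call.
- **General hand-in rule (6.F).** "Subjects will hand the sheets to their study coordinator at each visit and at the end of the study".
- **Use of the sheets (6.F).** "The data from these sheets will be used to assess compliance and adverse events in addition to information gathered from subjects". Section 3.B makes adverse event incidence and missed treatment days, each over both stages, the two primary outcomes.
- **After stopping (4.C).** "To the extent possible, participants who discontinue therapy will be followed to observe and record study outcomes". 8.E adds a study termination form, but only on voluntary withdrawal.
- **Analysis set (10.A).** The interim and final analyses "will also include those who dropped out or were withdrawn from the study before its completion". There is no rule for days with no returned sheet.

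**The concern.** A daily record that stays at home for six months is only as safe as the participant's last visit. Someone who withdraws or is lost in the food stage may have returned none of that stage's sheets. Nothing in the plan sets out how to get them, and daily doses and minor reactions cannot be reliably rebuilt later.

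The people most likely to leave may also be those with more reactions or poorer adherence. The food-stage estimates would then lean on those who finished. The gap is also uneven: in build-up, sheets come in about every two weeks. Aim 2 compares the two stages on safety and compliance, so unequal capture of the underlying records weakens that comparison directly.

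**Working it through.** The plan states no drop-out rate, expected missed-day rate or powered sample size, so there is no figure of its own to reproduce. The check has two parts.

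**1. Most days of sheets outstanding when a participant is lost**

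- Build-up (5.D.3): visits every 14 days, window up to +7, so 14 + 7 = 21 days.
- OIT maintenance (5.D and 5.D.4): no visit listed between the end of up-dosing and the end of the three months, so 365.25 / 4 ≈ 91 days.
- Food stage (5.D.5): one hand-in after six months, so 365.25 / 2 ≈ 183 days, half of the planned 12 months.

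Food against maintenance is 183 / 91 ≈ 2 to 1. Food against build-up is 183 / 21 ≈ 9 to 1. Stage 1 contains both build-up and maintenance.

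**2. What unreturned sheets do to the missed-day proportion**

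Let *p* be the proportion missed among days with a returned sheet, and *u* the share of planned days with none. If none of the unrecorded days was missed, the true proportion is *p*(1 − *u*). If all were missed, it is *p*(1 − *u*) + *u*.

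Assumptions: *p* = 5%; a share *d* of participants is lost at the end of the stage and returns nothing outstanding; everyone else returns everything. With hand-in at month 12 only, *u* = *d*. If sheets also came in at month 9, *u* = *d*/2. With monthly return, *u* = *d*/6. For the overall two-stage proportion under the current plan, stage 1 is taken as fully returned with the same *p*, so *u* = *d*/2.

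Example with *d* = 10%:

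- Month 12 only: 0.05 × 0.90 = 4.5%, and 4.5% + 10% = 14.5%.
- Monthly: *u* = 1.67%, so 0.05 × 0.9833 = 4.9%, and 4.92% + 1.67% = 6.6%.

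| Share returning nothing (assumed) | Food stage, month 12 only | Food stage, month 9 as well | Food stage, monthly | Overall, current plan |
|---|---|---|---|---|
| 5% | 4.75–9.75% | 4.9–7.4% | 5.0–5.8% | 4.9–7.4% |
| 10% | 4.5–14.5% | 4.75–9.75% | 4.9–6.6% | 4.75–9.75% |
| 20% | 4.0–24.0% | 4.5–14.5% | 4.8–8.2% | 4.5–14.5% |
| 30% | 3.5–33.5% | 4.25–19.25% | 4.75–9.75% | 4.25–19.25% |

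These are worst-case bounds, not expected biases. They show how little the returned data alone could rule out. Timing of loss matters: someone lost early has kept fewer sheets, and return of sheets cannot supply days after contact ends.

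**The case against.** The plan is not silent on people who leave, and several stronger readings that a reader might infer go too far.

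- **That anyone who stops takes the data with them.** Stopping is not loss. 4.C plans outcome follow-up after discontinuation, and 5.F brings back to the unit anyone who misses more than four consecutive days; under 6.F, sheets are handed in at a visit. This softens the point. But the follow-up is only as far as possible, and 5.F speaks partly of study protein, so its reach into the food stage is unclear. In that stage it would also depend on families reporting themselves, and scattered missed days would not trigger it.
- **That both primary outcomes are lost equally.** Adverse events can also surface through the 9-month interview, unsolicited contact (8.D), follow-up surveys (6.F) and SAE reporting. 8.A mentions a phone interview questionnaire, for pregnancy follow-up, whose content is not in the text, so it cannot be presumed empty. Against that, 8.D does not list the call as a source of adverse events. Missed days have much weaker cover.
- **That stage 1 is collected two-weekly throughout.** It is not; maintenance has a gap of about 91 days. The 9-to-1 contrast applies to build-up alone.
- **That the bias favours food by a known amount.** Suppose 80 people enter the stage, 10% to 20% leave at uniform times and leavers have 2 to 5 times the finishers' event rate. The leavers' days are then 8 × 91.5 = 732 of 13,908 (5.3%) to 16 × 91.5 = 1,464 of 13,176 (11.1%). With *w* that share and *r* the rate ratio, 1 − 1/((1 − *w*) + *rw*) gives an understatement of 5% to 31%. None of those inputs is in the documents, and the sum assumes that no leaver's event is captured by any route. If leavers' events were reported but their dosing days were not, the rate could be biased upward.

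It is also fair to say that this is an uncontrolled estimation study with no hypothesis tests. That lowers the stakes. It does not remove them, because the estimates are the study's product.

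**Conclusion.** The point holds in a limited form. Month 12 is the only scheduled collection of food-stage sheets, and no step retrieves them at withdrawal or loss. Up to about 183 days of daily records per participant may go unreturned, roughly twice the maintenance maximum and nine times the build-up maximum. The missed-day primary outcome is most exposed; adverse events are partly covered elsewhere.

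Stage-2 and overall estimates may be biased, probably but not certainly in favour of food, and the Aim 2 comparison is weakened by unequal capture. The direction rests on leavers doing worse than finishers, which is plausible but not shown. The size depends on drop-out, which the documents do not give; the table is illustrative, with *p* and *d* both assumed. The change is worth making because it is cheap and the lost records cannot be recovered at analysis.

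**What to change.** - **5.D.4, 5.D.5 and 6.F:** have maintenance and food-stage sheets sent in monthly by photograph, email or post. The sheets already change weekly and families already have staff email addresses.
- **5.D and 5.D.5:** state what the 9-month interview records, and have the coordinator record the sheet data to date at that call.
- **4.C:** at any discontinuation or first failed contact, require an attempt to collect outstanding sheets and to record the last dose date, the reason, and adverse events since the last returned sheet.

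This takes a small protocol amendment and some coordinator time each month. It needs no new visit, procedure or staff and leaves treatment unchanged. The downside is a small burden on families and coordinators, and possibly a less favourable food-stage estimate.
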